3.2 SECONDARY OBJECTIVES

Evaluation of the impact of moderate hypothermia on:

- Mortality during hospitalization and up to 180 days
- VA-ECMO weaning time
- Adverse cardiovascular events
- Necessity of fluid and vasopressor (norepinephrine, epinephrine)
- Lactate clearance
- Duration of organ failure
- Mechanical ventilation support use
- Renal replacement therapy use
- Duration of ICU stay and total duration of hospitalization
- The risk of bleeding
- The risk of Sepsis (pulmonary, blood, venous lines, VA-ECMO cannulaes)

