3.3 STUDY OUCOME MEASURES

3.3.1 **Primary endpoints**

All-cause mortality at day 30 following randomization (i.e. 30 day mortality)

3.3.2 **Secondary endpoints:**

[figure not shown]
- All-cause mortality at 48 hours and day 7, 60, 180
- VA-ECMO duration
- Composite endpoint of death, cardiac transplant, escalation to LVAD, stroke at days 30, 60, 180
- Cumulated amount of administered fluids and duration of vasopressors use in ICU
- Duration to normalization of lactate
- Number of days alive without organ failure(s), defined with the SOFA score and its components (respiratory, liver, coagulation and renal), between inclusion, D7 and D30
- Duration of mechanical ventilation and the number of days between inclusion and day 30/ day 60/ day 180, alive without mechanical ventilation
- Number of days alive without renal replacement therapy, and the number of days, between inclusion and day 30, day 60 and day 180, without renal replacement therapy

- Duration of ICU stay, of hospitalization
- Number of severe and moderate bleeding complications (GUSTO-definition, N Engl J Med. 1993;329:673–682) and the number of packed red blood cells transfused under VA-ECMO
- Infection probability: pulmonary, blood and VA-ECMO cannulaes

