7 SAFETY ASSESSMENT

7.1 DESCRIPTION OF SAFETY ASSESSMENT PARAMETERS, METHOD AND CALENDAR USED FOR THE EVALUATION OF SAFETY

In both group, the VA-ECMO implementation and monitoring will be done in accordance with the current standard of care. All adverse events will be documented during this study from medical examinations, biological and imaging exams if necessary and will be complied in the electronic case report form (eCRF).

In particular, glycaemia, blood gas and coagulation will be followed up and the occurrence of shivering, modifications in blood gas management, hyperglycemia, electrocardiographic changes, mild coagulopathy and increased sensitivity to infection will all be recorded as adverse events.

Uncontrolled bleeding and coagulation disorders that require blood cells or platelet transfusion will be considered as serious events.

In normothermia group, no additional risk linked to research is expected.

All adverse events between inclusion and D7 will be recorded.

After D7, only serious life-threatening and fatal adverse events will be recorded until the end of the follow-up of the patient.

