11.1.2 Statistical analysis for the secondary endpoints

For the secondary analysis of a) all-cause mortality at 48 hours and day 7, 60, 180, b) the composite endpoint of death, cardiac transplant, escalation to LVAD, stroke at days 30, 60, 180 the same analysis strategy will be performed as for the primary endpoint.

Unpaired t-test will be performed, after checking for normality of the variable's distribution, for the outcomes mentioned below. Importantly, In case of non-normal distributions (which is highly likely for all duration data), non-parametric tests will be performed.

- VA-ECMO duration
- cumulated amount of administered fluids and duration of vasopressors use
- duration to normalization of lactate
- Number of days alive without organ failure(s), defined with the SOFA score and its components (respiratory, liver, coagulation and renal), between inclusion, D7 and D30
- duration of mechanical ventilation and the number of days, between inclusion and day 30/ day 60/ day 180, alive without a mechanical ventilation
- number of days alive without renal replacement therapy, and the number of days, between inclusion and day 30/ day 60/ day 180, without renal replacement therapy
- duration of ICU stay, of hospitalization
- number of severe and moderate bleeding complications (gusto-definition) and number of packed red blood cells transfused under VA-ECMO

Chi-square tests (or Fisher exact test in case of insufficient number of expected patients in on of the 2x2 cell) will be performed for the outcomes mentioned below:

- Pulmonary, blood and VA-ECMO cannulaes infections

To illustrate the association, an odd-ratio will be provided.

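### Infection is compared as a crude ever/never proportion with no time horizon, so infection risk while alive is mixed with survival; separately, its sites do not match the objective

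*Protocol*

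**What the plan says.** - **Objective (3.2):** "The risk of Sepsis (pulmonary, blood, venous lines, VA-ECMO cannulaes", that is, four sites.
- **Endpoint (3.3.2):** "Infection probability: pulmonary, blood and VA-ECMO cannulaes", that is, three sites and no time point.
- **Analysis (11.1.2):** "Chi-square tests (or Fisher exact test in case of insufficient number of expected patients in on of the 2x2 cell" is the method, applied to "Pulmonary, blood and VA-ECMO cannulaes infections". On the effect measure: "To illustrate the association, an odd-ratio will be provided". Death before infection is not mentioned.
- **Contrast within 11.1.2:** other outcomes do carry horizons, and some count only days alive, for example "day 60/ day 180, alive without a mechanical ventilation".
- **Recording (7.1):** heightened susceptibility to infection is among the events to be recorded as adverse events. The window is "All adverse events between inclusion and D7 will be recorded", and then "After D7, only serious life-threatening and fatal adverse events will be recorded until the end of the follow-up of the patient".
- **Recording (7.2.2):** the occurrence of nosocomial infection is entered in the eCRF. No time limit is given, and no date is mentioned. Section 7.2.4 mentions event dates, for non-serious events.
- **Relevance:** sections 1.2, 1.4.2 and 7.2.2 all name infection as a possible side effect of hypothermia.

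**The concern.** A patient who dies on day 2 has had two days in which to become infected; a patient alive at day 30 has had thirty. With about half the control arm expected to die by day 30, the ever-infected proportion depends on survival as well as on susceptibility. Suppose hypothermia saves lives and leaves the daily infection risk unchanged. Its patients are then exposed for longer, and the odds ratio moves above 1. Suppose instead that it raises mortality. Exposure is then cut short, and a true rise in infection risk can be masked. Either way, the planned comparison does not directly answer whether cooling makes patients more prone to infection, which is the harm the protocol names.

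The missing horizon adds to this. Section 7.1 points to day 7 for complete adverse event recording, while 7.2.2 sets no limit, so two analysts could count different events. A further, unrelated point is that venous lines appear in the objective but not in the endpoint or its analysis.

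**Working it through.** **Plan's own figure.** The protocol gives no figure for infection. The mortality inputs come from the sample size in 11.2: 50% in controls, a 15-point absolute reduction (so 35%), 80% power, two-sided 5%, 167 per group. With unpooled variances:

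n = (1.960 + 0.842)² × (0.50×0.50 + 0.35×0.65) / 0.15² = 7.849 × 0.4775 / 0.0225 ≈ 166.6, so 167. This reproduces. The pooled-variance formula gives 170.

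**Assumptions, not in the protocol.** The daily infection hazard while alive is λ = 0.01, 0.03 or 0.05, the same in both arms. The horizon is day 30 or day 7. Death times are either constant-hazard or front-loaded.

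**Constant death hazard.** μ = −ln(1 − mortality)/30, which is 0.02310 per day for controls and 0.01436 for hypothermia. The ever-infected proportion by day H is

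λ/(λ+μ) × [1 − exp(−(λ+μ)H)].

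For λ = 0.03 and H = 30:
- Control: 0.5649 × (1 − e^−1.593) = 0.5649 × 0.7967 = 45.0%.
- Hypothermia: 0.6763 × (1 − e^−1.331) = 0.6763 × 0.7357 = 49.8%.
- Odds ratio: 1.21, where the true ratio of infection hazards is 1.

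| λ per day | Control, day 30 | Hypothermia, day 30 | Odds ratio |
|---|---|---|---|
| 0.01 | 19.0% | 21.3% | 1.15 |
| 0.03 | 45.0% | 49.8% | 1.21 |
| 0.05 | 60.8% | 66.4% | 1.28 |

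**Front-loaded deaths.** Among those who die by day 30, death times follow an exponential with scale d = 3, 5 or 10 days, truncated at day 30. With μ = 1/d, the chance that such a patient is infected before death is

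1 − [μ/(λ+μ)] × [1 − e^(−30(λ+μ))] / [1 − e^(−30μ)].

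A survivor's chance is 1 − e^(−30λ). For λ = 0.03 and d = 5 these are 0.129 and 0.593:
- Control: 0.50×0.129 + 0.50×0.593 = 36.1%.
- Hypothermia: 0.35×0.129 + 0.65×0.593 = 43.1%.
- Odds ratio: 1.34.

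Over d = 3 to 10 and λ = 0.01 to 0.05, the day-30 odds ratio is 1.20 to 1.48.

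**All scenarios together.** The last column uses a chi-square test with 167 per group at the 4.9% level of section 11.3, by normal approximation. The nominal chance in that direction is 2.45%.

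| Horizon | Excess in hypothermia arm | Odds ratio | Chance of a significant result against hypothermia |
|---|---|---|---|
| Day 30 | 2.3 to 9.7 points | 1.15 to 1.48 | 7% to 42% |
| Day 7 | 0.2 to 2.6 points | 1.03 to 1.16 | 3% to 8% |

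**Reverse direction.** If the two mortalities are swapped, the odds ratios invert. At 3% per day with constant hazards, 1/1.21 ≈ 0.83, so unchanged infection risk would look protective.

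**The case against.** **The crude proportion is a legitimate quantity.** Vital status is collected for every patient (4.1.9). With complete follow-up to a fixed horizon, the ever-infected proportion is identical to the cumulative incidence with death as a competing event. This stands, and it has a consequence: a reader might infer that a competing-risk cumulative incidence would cure the problem, but it would return the same 45.0% and 49.8%. Only a comparison of rates while alive separates the two effects. The planned test is therefore not invalid; it answers a different question from the one about susceptibility.

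**The size rests on assumptions.** The protocol gives no infection rate, and the calculation takes the full 15-point mortality benefit. With no mortality difference and the same timing of deaths, the artefact vanishes. Cannula infection is tied to having cannulae in place, so a hazard running unchanged to day 30 suits that site poorly. At day 7 the effect is small. All of this stands and limits the size, but not the direction.

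**The SAP may settle it.** A horizon and further methods can be set there, so their absence alone would not be a finding. What this protocol does fix is the test, the odds ratio, two recording rules that point to different windows, and two site lists that disagree.

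**Venous lines are a small matter.** A reader might infer that the missing site contributes to the survival bias. It does not; it is a separate mismatch. Nor is it clear that line infections go uncounted, since some may be classed under blood and 7.2.2 does not restrict the site.

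**Survival is reported alongside.** Mortality at several time points and Kaplan-Meier curves (11.1.1, 11.1.2) let a careful reader see differing exposure, but they do not quantify its effect on the infection comparison.

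**Conclusion.** The point holds with limited scope. As written, the infection comparison mixes infection risk while alive with time at risk, over a period the protocol does not settle. Under the trial's own mortality hypothesis and equal daily infection risk, the crude odds ratio exceeds 1 in every scenario examined. At day 30 it is about 1.15 to 1.28 with constant death hazards and assumed rates of 1 to 5% per day, and up to 1.48 with early deaths. At day 7 the distortion is minor. If mortality rose instead, real harm could be obscured.

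It would go too far to say that any survival benefit will show as an infection harm: even in the least favourable scenario the chance of a significant false signal is 42%, and in most it is well below that. The four-site versus three-site discrepancy is real, but it is a matter of wording to reconcile. Infection is a secondary endpoint and the primary mortality result is unaffected. The reason to act is that infection is a named risk of the intervention and the improvement is cheap.

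**What to change.** 1. In 3.3.2 and 11.1.2, state one horizon for infection, consistent with the recording windows in 7.1 and 7.2.2.
2. In 11.1.2, report the cause-specific hazard ratio for first infection (time to first infection, censored at death and at the horizon) beside the crude proportion or cumulative incidence and its chi-square or Fisher test. The two should be read together: one describes the infection burden among randomised patients, the other the rate while alive. The hazard ratio removes the difference in exposure time, but not any difference in frailty among patients kept alive.
3. Confirm that infection dates are captured to the chosen horizon. This cannot be taken as given: 7.2.2 records occurrence only, 7.2.4 gives dates for non-serious events, and 7.1 restricts adverse event recording after day 7.
4. Separately, reconcile the sites in 3.2 with those in 3.3.2 and 11.1.2, and in the synopsis. Either include venous lines throughout or say where they are counted, and use either sepsis or infection consistently.

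The cost is text in a few sections, one extra model and, if the horizon lies beyond day 7, possibly the collection of infection dates after that day.

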11.2 SAMPLE SIZE CONSIDERATION

We considered that mortality in cardiogenic patients supported with VA-ECMO will be 50% (based both on ELSO data, [name] data (*Crit Care Med.* 2008 May;36(5):1404-11) and study principal investigator's personal data (database of 150 patients)

The objective of the study is to demonstrate the superiority of the treatment with VA-ECMO plus moderate hypothermia as compared to VA-ECMO alone on mortality.

Therefore, considering a total event risk (for the primary endpoint) of 50 % in the control group, a sample size of N = 167 patients/group will detecting a 15% absolute difference in favor the VA-ECMO group using a chi-square test with a 80 % power and considering a two-sided global alpha level of 5% using the LanDe Mets method with O'BrienFleming boundary for one interim analysis (efficacy and futility) after inclusion of 2/3 of the patients.

11.3 DEGREES OF STATISTICAL SIGNIFICANCE

A bilateral p value lower than 4.9% will be considered significant for the final analysis. A p value threshold lower than 5% is mandatory given the planned interim analyses to ensure a global alpha level at 5%.

11.4 PLANNED INTERIM ANALYSES (IF APPLICABLE)

One interim analysis for efficacy/futility will be performed after inclusion of 2/3 of the patients.

De-identified hospitalization reports will be collected from the associated centers. These reports will be centralized at the CIC-P of the CHRU of Nancy and will be submitted to a reading committee.

11.5 STATISTICAL CRITERIA FOR STUDY TERMINATION

A p-value threshold of 0.001 will be used for this interim analysis as calculated with the LanDe Mets method with O'BrienFleming boundary.

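### The interim threshold of p<0.001 is not the Lan-DeMets O'Brien-Fleming value at two thirds of the patients (0.0121), so the named method and the stated stopping numbers contradict each other

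*Protocol*

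**What the plan says.** Four places in the Protocol define the group-sequential rule.

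- Section 11.2 (repeated under study size in the synopsis) sets a two-sided 5% global alpha "using the LanDe Mets method with O'BrienFleming boundary for one interim analysis (efficacy and futility) after inclusion of 2/3 of the patients".
- Section 11.4 repeats the timing: "One interim analysis for efficacy/futility will be performed after inclusion of 2/3 of the patients".
- Section 11.5 gives the interim number and its source: "A p-value threshold of 0.001 will be used for this interim analysis as calculated with the LanDe Mets method with O'BrienFleming boundary".
- Section 11.3 gives the final number: "A bilateral p value lower than 4.9% will be considered significant for the final analysis". The reason given there is that "A p value threshold lower than 5% is mandatory given the planned interim analyses to ensure a global alpha level at 5"%.

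Only the interim 0.001 is attributed to the Lan-DeMets O'Brien-Fleming method in its own sentence. Section 11.3 names no method. The 0.049 is tied to it because section 11.2 says that this method is how the 5% global level is kept.

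**The concern.** A spending function, an overall alpha and an information fraction determine the boundary completely. The Protocol fixes all three and then states a number that they should produce. An O'Brien-Fleming-type boundary is strict early and relaxes as information accrues. A threshold of 0.001 looks too strict for a look as late as two thirds, and a final level of 0.049 looks too generous after such a look.

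If so, the Protocol holds two decision rules for a mortality endpoint. The monitoring board's statistician could follow the stated number or recompute the boundary from the named method, and either could be defended from the text. The two rules disagree over a wide band of interim results and a narrow band of final ones. A choice made after unblinded data are seen would depend on those data.

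**Working it through.** **Inputs (sections 11.2 to 11.5).** Two-sided alpha 0.05; one interim; information fraction t = 2/3; 167 per group; 50% v 35% mortality; chi-square test; stated thresholds 0.001 and 0.049.

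**1. The plan's sample size reproduces.** Unpooled formula: n = (1.960 + 0.842)² × (0.50×0.50 + 0.35×0.65) / 0.15² = 7.849 × 0.4775 / 0.0225 = 166.6, so 167 per group. The pooled formula gives 170.

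**2. Interim boundary from the named method.** With 0.025 per side, the two-sided alpha spent by fraction t is 4 × [1 − Φ(2.2414/√t)]. At t = 2/3, 2.2414/0.8165 = 2.745, and the alpha spent is 0.0121. The interim rule is therefore p<0.0121 (|Z|>2.509).

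**3. Final boundary.** The interim and final Z are bivariate normal with correlation √(2/3). Solving for the final critical value that makes overall two-sided alpha 0.05 gives |Z|>1.993, that is p<0.0463.

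**4. Can another timing or variant produce 0.001 and 0.049?**

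| Rule | Interim p | Final p |
|---|---|---|
| Stated | 0.001 | 0.049 |
| Named method, t = 2/3 | 0.0121 | 0.0463 |
| Named method, t = 0.60 | 0.0076 | 0.0476 |
| Named method, t = 0.50 | 0.0031 | 0.0490 |
| Named method, t = 0.415 | 0.0010 | 0.0497 |
| Spending on 0.05 two-sided, t = 2/3 | 0.0164 | 0.0439 |
| Classic O'Brien-Fleming, t = 2/3 | 0.0142 | 0.0452 |

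No row reproduces the pair. The 0.001 needs t of about 0.41 and the 0.049 needs t = 0.50. The t = 0.60 row allows for patients who are included but have not yet reached day 30. The stated pair does add to 0.001 + 0.049 = 0.05, which is what a simple split of alpha would give.

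**5. Error rate of the stated pair.** Using 0.001 at t = 2/3 and 0.049 at the end, the same bivariate normal gives an overall two-sided alpha of 0.0491. After spending 0.001, the exact final level would be 0.0499.

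**6. Operating characteristics at 50% v 35%** (2,000,000 simulated trials, 111 then 167 per arm, pooled chi-square):

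| | 0.001 / 0.049 | 0.0121 / 0.0463 |
|---|---|---|
| Chance of stopping for efficacy at the interim | 15% | 40% |
| Overall power | 80.2% | 78.9% |

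The interim p lies between the two thresholds in about 26% of trials. A normal approximation with unpooled variance gives 16% and 41% for stopping, and 79.9% and 79.6% for power.

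**7. In deaths.** Around the average rate of 42.5%, the standard error of the difference in deaths between two arms of 111 is √(2 × 111 × 0.425 × 0.575) = 7.37. A difference of 19 gives Z = 2.58 (p = 0.0099) and passes 0.0121; 18 gives p = 0.0145 and does not. A difference of 24 gives p = 0.0011 and just misses 0.001, so 25 is needed. The interim hurdle is about 25 deaths under the number and 19 under the method.

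**The case against.** The best defence is that the Protocol states one explicit number for each analysis, and together they work. Overall alpha is 0.0491, the promised 5% is kept, and power is about 80% as stated. A strict interim threshold is conservative for type I error. About 99% of trials whose interim p falls between 0.001 and 0.0121 still finish with p<0.049, so the eventual conclusion rarely changes; what changes is whether the last third is enrolled. All of this stands, and it limits the point.

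A reader might infer three stronger things that the document does not support.

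- **Inflated alpha.** Pairing 0.0121 at the interim with 0.049 at the end gives 0.0526. The Protocol never states 0.0121 and no section directs that pairing, so this describes a possible misuse and not the written rule.
- **Too small a sample.** Under the written thresholds, 167 per group delivers the stated power. Even under the named method's boundary, power is about 79%.
- **A missing futility rule.** Sections 11.2 and 11.4 describe the look as serving efficacy and futility, and section 11.5 gives one p-value. Section 11.5 does not say that this p-value decides futility, and a futility boundary may properly sit in a statistical analysis plan that is not at hand.

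The defence does not reach section 11.5's statement of how 0.001 was obtained. That statement is wrong for the stated timing and for every timing and variant tried that would also give 0.049.

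**Conclusion.** The point holds as a contradiction between the named method and the stated numbers. With one look at two thirds of the information and two-sided alpha of 5%, Lan-DeMets O'Brien-Fleming gives 0.0121 and 0.0463, against the stated 0.001 and 0.049. The interim figure is about 12 times stricter than the method it is credited to.

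The practical consequence is an ambiguous stopping decision in roughly one trial in four if the design effect is real, and an ambiguous final result if p falls between 0.0463 and 0.049. The boundary values assume that the information fraction equals the fraction of patients, which is reasonable for a binary 30-day endpoint; at 60% information the mismatch remains. The stopping probabilities assume 50% v 35% mortality with 111 patients per arm at the interim.

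**What to change.** Before the interim analysis, choose one rule and make the synopsis (study size) and sections 11.2, 11.3 and 11.5 agree.

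- **(a) Keep the method.** Retain Lan-DeMets O'Brien-Fleming, state p<0.0121 at the interim and p<0.0463 at the end, and say that both will be recomputed from the information fraction actually reached. Restate power as about 79% at 167 per group. The cost is a slightly stricter final level and a slightly lower stated power.
- **(b) Keep the numbers.** Retain 0.001 and 0.049, describe them as a Haybittle-Peto-type rule, and delete the Lan-DeMets O'Brien-Fleming attribution wherever it appears. Sample size and stated power stay as they are.

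Both are wording changes with no effect on recruitment or data collection. Option (b) disturbs least, because it leaves every number in the Protocol in place.

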11.6 METHOD FOR ADDRESSING MISSING, INVALID OR UNUSED DATA

For the primary outcome, we do not expect missing variables. All-cause 30 days mortality is a straightforward outcome that does not require detailed information. Yet, in the unlikely case of missing vital status at 30 days, patients with missing data will be analyzed with the last observation being carried forward. In a sensitivity analysis, the worst case scenario method will be used (i.e. all patients with incomplete follow-up data died in the intervention group and died in the no intervention group).

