4.3 BIAS CONSIDERATION

4.3.1 Randomization procedure

Randomization will be performed after enrolment using a centralized on-line randomization system (Cleanweb[™]) available 24h/24h.

Treatments arms :

- **Experimental group:** Patients with CS allocated to a strategy of moderate hypothermia (33°C≤ T°C ≤34°C) associated with usual care.
- Control group: Patients with CS allocated to a strategy of normothermia 36°C≤ T°C ≤37°C associated with usual care.

Randomization will be stratified on the center. The randomization plan will be devised by Centre investigation Clinique 1433 module Plurithématique de Nancy, France.

4.3.2 **Replacement procedures for patients**

All patients non randomized will be replaced to reach 334 patients (167 patients in each group) (cf chapter 11.8)

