11 DATA ANALYSIS AND STATISTICAL DETERMINATION

11.1 DESCRIPTION OF ANTICIPATED STATISTICAL ANALYSIS METHODS

11.1.1 Statistical analysis for the primary endpoint

The differences between the 2 study groups (i.e. intervention and controls) in the risk of all-cause mortality at day 30 following randomization will be studied using the Chi-2 test. To illustrate the association, both an odd-ratio and a hazard ratio will be provided. In addition, survival curves using the Kaplan-Meier method will be constructed.

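### Last observation carried forward for day-30 vital status always imputes survival, and the stated sensitivity analysis does not test the differential worst case

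*Protocol*

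**What the plan says.** The primary endpoint (Protocol section 3.3.1) is "All-cause mortality at day 30 following randomization (i.e. 30 day mortality"). Section 11.1.1 tests it as a binary outcome: "all-cause mortality at day 30 following randomization will be studied using the Chi-2 test". The odds ratio, hazard ratio and Kaplan-Meier curves only illustrate the result. Section 11.8 puts every randomized patient in the analysis.

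Section 11.6 expects no missing day-30 status. If some is missing, "patients with missing data will be analyzed with the last observation being carried forward". One sensitivity analysis follows, labelled worst case, in which every patient with incomplete follow-up is counted as dead in both arms.

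Section 4.1.9 collects vital status, with date and cause of death, at 48 hours and days 7, 30, 60 and 180. The patient, the family or the primary care physician is contacted where needed. Section 11.6 does not say that the later contacts settle an unknown day-30 status before the rule applies.

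**The concern.** Carrying the last value forward for a terminal event is single imputation of one outcome. A patient last seen alive on day 7 enters the chi-square table as a day-30 survivor with the same certainty as one examined on day 30. Mortality is understated in any arm with missing patients. If loss differs between arms, the comparison shifts towards the arm with more loss.

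The trial is open, so loss can depend on allocation. Section 4.5.1 lets a patient leave at any time and lets an objection bar use of the data. Section 13.2 lets the patient, family or support person withdraw consent. These are the realistic routes to missing status. At stake is the primary result, because the rule feeds the primary test directly.

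**Working it through.** **Inputs.** Control risk: "considering a total event risk (for the primary endpoint) of 50 % in the control group" (section 11.2). Effect: "15% absolute difference", so 50% v 35%. Size: 167 per group (sections 4.3.2 and 11.2), "using a chi-square test with a 80 % power". Final two-sided level: 0.049 (section 11.3). The missing share and the death risk among missing patients are assumptions, since the protocol gives neither.

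**Plan's own figure.** The unpooled formula gives n = (1.960 + 0.842)² × (0.50×0.50 + 0.35×0.65) / 0.15² = 166.6, so 167 per group. The stated size is reproduced. With the pooled-variance test at level 0.049, 167 per group has 79.2% power.

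**What the rule does.** Observed risk = true risk − (missing share × death risk among the missing). Let the missing die at 50% to 100% of their arm's risk.

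*Equal missingness, true effect present:*

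| Missing, both arms | Observed risks | Difference (points) | Power |
|---|---|---|---|
| 0% | 50.0% v 35.0% | 15.0 | 79.2% |
| 2% | 49.5% v 34.65% to 49.0% v 34.3% | 14.9 to 14.7 | 78.5% to 77.8% |
| 5% | 48.75% v 34.1% to 47.5% v 33.25% | 14.6 to 14.3 | 77.4% to 75.6% |

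*Unequal missingness, no true effect (50% in both arms; none missing in control, 5% in hypothermia):* the spurious benefit is 0.05 × 0.25 = 1.25 points to 0.05 × 0.50 = 2.5 points. The standard error is about 5.47 points, so the shift is 0.23 to 0.46 standard errors. Two-sided rejection at a nominal 4.9% becomes 5.5% to 7.3%.

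**Near the boundary.** Uncorrected chi-square with 83 control deaths of 167:

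- 65 hypothermia deaths: p = 0.047, significant at 0.049.
- 66 hypothermia deaths: p = 0.061, not significant.

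One hypothermia death carried forward as alive can decide the result. Each such death moves that arm's mortality by 1/167 = 0.6 points.

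**What the sensitivity analysis does.** Let d be recorded deaths and m missing patients, with subscripts C (control) and H (hypothermia). The mortality difference, control minus hypothermia, times 167 is:

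- last observation carried forward: d_C − d_H
- stated sensitivity analysis: d_C − d_H + (m_C − m_H)
- differential worst case: d_C − d_H − m_H

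With equal missing counts the stated analysis gives the same difference as the primary rule. With more missing in control it gives a larger benefit. It matches the differential worst case only when m_C = 0.

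**The case against.** The strongest reply is that little will be missing. Patients are intubated and on VA-ECMO at entry, vital status is simple to obtain, and section 4.1.9 provides tracing. At 2% equal missingness the power loss is about 0.7 to 1.4 points. The type I inflation above needs an assumed 5% v 0% imbalance. This stands and limits the size of the point. It does not defend the rule, which matters only when status is missing.

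A second reply is that the primary rule counts all unknowns as alive and the sensitivity analysis counts them all as dead, so overall mortality is bracketed. This is true of each arm's mortality but not, in general, of the difference between arms.

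A third is that multiple imputation and Kaplan-Meier carry their own assumptions, and Kaplan-Meier needs non-informative censoring. This is fair, but either is less extreme than giving every unknown patient certain survival.

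A reader might also infer that the ±5-day window hides deaths on days 26 to 30. The protocol largely answers this: the date of death is collected, and the day-60 and day-180 contacts recover such deaths. A gap remains only for a patient contacted on days 25 to 29 and never reached again.

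A reader might likewise infer from "One interim analysis for efficacy/futility will be performed after inclusion of 2/3 of the patients" (section 11.4) that recent patients are counted as alive at the interim. At uniform accrual, 334/36 = 9.3 per month, about 9 of 223 patients would be short of day 30 if data were cut at that inclusion. The protocol sets no such cut and does not apply the missing-data rule to patients not yet due.

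**Conclusion.** The point holds for the missing-data rule. Section 11.6 fixes survival as the imputed value for every unknown day-30 status in the primary analysis, and its one sensitivity analysis does not in general test the scenario that would challenge a claimed benefit.

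The expected size is small: a power loss of about 1 point at 2% missing in both arms. It becomes material at about 5% missing or more, when loss is unequal, or when the result lies within a death or so of the boundary. The missing shares, and the 50–100% relative death risk among the missing, are assumptions.

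It would be tempting to say that five lost patients in one arm move the difference by 3 points (5/167). That needs all five to have died. At 50% mortality the expected shift is 1.5 points. The visit window and the interim trigger are at most minor clarifications and not part of this conclusion.

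**What to change.** - Define the endpoint as death on or before day 30 after randomization, by date of death.
- State that the day-60 and day-180 contacts settle an unknown day-30 status before any missing-data rule applies.
- For patients still unknown, use multiple imputation, or censor at last contact and compare Kaplan-Meier day-30 risks. State which of the two is primary. Keep last observation carried forward at most as a sensitivity analysis.
- Make the worst case differential: missing hypothermia patients dead, missing control patients alive.

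The cost is a change of wording and slightly more analysis work. No new data are needed, because dates of death and the later contacts are already planned, and the sample size is unchanged. If Kaplan-Meier is chosen, the primary comparison is no longer a plain chi-square test and section 11.1.1 must say so.
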